Randomization: Patients will be adaptively randomized, based on age (50-64 years and 65-85 years), and severity (severe – ARAT > 35, non-severe – ARAT <= 35), to two groups – the active FES group receiving intervention with the active FES (n = 72) and the passive FES group receiving FES only intervention (n=72). Advancing age has a major negative impact on stroke morbidity, mortality; older adults (> 65 years) have increased chance of dying after stroke and being discharged to the skilled nursing facility if they survive, therefore age 65 will be used as a cut-off. There is some evidence that patients with ARAT scores above or below 35 show clear differences in recovery [41], therefore ARAT of 35 will be used as a cutoff.

Subject identification and Recruitment

Subject Identification:

- a) Through referrals by the Stroke Neurology team or other UWHC or UW Rehab hospital or The American Center (TAC) clinicians involved in patient care, in the in-patient or outpatient setting.
- b) Clinicians involved in the care of patients may send recruitment letters to eligible patients and ascertain their interest in study participation.
- c) A stroke service patient log maintained by the UW-Madison Stroke Neurology section UWHC or UW Rehab hospital or TAC clinicians will be used to identify patients.
- d) By posting recruitment flyers in community newsletter, at different locations such as the UWHC, the School of Medicine, UW libraries, the University Station Clinic, St. Mary's hospital, Meriter hospital, as well as UW out-patient clinics and rehab centers outside the Madison area, Madison public libraries, stroke support and other aging support group locations, and on the Principal Investigator, [name] lab

webpage <http://radiology.wisc.edu/research/>. We will also release ads regarding recruitment in the media – in major newspapers such as the Wisconsin State Journal, the Milwaukee Sentinel, in the Isthmus, and through the Wisconsin Public Radio (WPR).

e) [name], the radiologist involved in clinical imaging protocols of patients, will identify patients who are suitable for study participation as they present to the UWHC, UWMF, WIMR, or Health Emotions Research Institute (HERI) for clinical imaging.

f) We have permission to contact participants who have participated in other stroke research conducted by our group ([name] 2013-1561, 2015-0469 and 2018-0398). We propose to contact these patients and ascertain interest in participating in this study.

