Active FES (the experimental group): Training will involve trials of actual or attempted hand movement alternating with periods of rest. Patients will be trained to control a cursor on a computer screen using motor-related cortical activity. EEG electrodes will be attached to the patient’s scalp using a standard, commercially available electrode cap. We will use the general purpose, freely available BCI computer program “BCI2000” to control signal acquisition, signal processing, and feedback to the participant. The EEG-BCI system will be connected to a FES device and the FES electrodes will be placed on the stroke-affected arm. Electrode placement is similar to that described above for the patients in the passive FES group. The electrodes will be connected to commercially available stimulus isolator units, which ensure clean, opto-electrical isolation. The aim is to elicit motor response in the affected hand in all of the

fingers as evenly as possible. The appropriate level of stimulation that is both comfortable for the participant and sufficiently produces visible movement in the affected hand is estimated and recorded for use in the current and future sessions. All patients will complete 2-3 study visits per week (up to a maximum of 15 sessions) with each session or study visit lasting for about 2 hours.

Study procedures [behavioral visits and intervention] will be photographed and visibly and audibly recorded. Permission will be obtained from the participant before photographs/recording are commenced. The pictures/recording may be used in the following ways:

- in lab meetings to discuss the participant's progress and possible ways to improve testing
- to assess inter-tester reliability and for training new personnel before they administer the behavioral tests
- in research group presentations with collaborators or at conferences to show examples of participants performing the tasks in this research study

Compensation for study participation

All patients will be compensated up to \$500 for completing the entire study. Payment of up to \$100 (\$60 for completing the MRI scan and \$40 for completing the behavioral testing) will be provided at the end of each of the five study assessment time-points.

Note since MR scanning is optional, we will offer \$60 for each MR scan and \$40 for each behavioral assessment/testing session at each visit (\$60 for MR scan + \$40 for assessment/testing = \$100 per visit X 5 = \$500).

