All researchers and research staff involved in the study have completed Human Subjects and HIPAA training and will be continuously involved in data and safety monitoring. Data and safety monitoring will occur on a continuous basis. fMRI and EEG data will be reviewed by the PI, Co-I and a group of study team members on a continuous basis. All behavioral measures (e.g., ARAT, 9 holepegboard task, SIS etc.) will be reviewed by the study team within a week or two of collection.

Data Processing/Data Analysis

For Specific Aim 1:

1a) To investigate the efficacy of active FES vs. passive FES, as measured by changes in behavioral measures. A linear mixed model analysis in SPSS 22.0 will be run for each dependent measure (e.g., ARAT, SISand function) with Group (active, passive) as the between-participant factor and Time (baseline, mid, post, 1 month post) as the within-participant factor. The two baseline assessments will be averaged so as to get a stable measure of baseline performance prior to receiving intervention.

1b) To investigate the impact of BCI synchronized to FES on behavioral outcomes in the patients in the Active FES group: A post hoc analysis will be done to evaluate whether high-performers of the BCI classification task show more improvement in behavioral measures than low-performers of the BCI classification task. This will allow us to assess to what extent BCI synchronization to FES leads to improved stroke recovery. A median split of high to low performers on the BCI task will be done. We will then compare change in outcome measures of those with high performance on the BCI task (which is synchronized to FES) vs. those with low performance on the BCI task (when there is less synchronization between the BCI and FES) using unpaired t-tests. If there is a difference in the two groups then this is evidence that BCI synchronized to FES contributes to recovery, if there is no difference then this is evidence that BCI irrespective of synchronization to FES contributes to recovery.

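### Item 1b counts any outcome difference between high and low BCI performers as evidence that synchronization aids recovery, although recovery itself or a shared cause can produce that difference

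*Combined protocol and SAP*

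**What the plan says.** The Data Processing/Data Analysis section, Specific Aim 1, item 1b, is confined to the active FES arm. The exposure is dichotomised: "A median split of high to low performers on the BCI task will be done". The comparison follows: "We will then compare change in outcome measures of those with high performance on the BCI task" against low performers, "using unpaired t-tests". The stated purpose is to learn how far synchronization brings about better recovery, and the reading of the result is fixed beforehand: "If there is a difference in the two groups then this is evidence that BCI synchronized to FES contributes to recovery". A companion rule reads the absence of a difference as evidence that BCI helps whether or not it is synchronized to FES.

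Item 1b does not say which sessions define performance or which interval defines change. It names no covariate. It is labelled post hoc.

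The Intervention section describes the BCI task as part of active training: "Patients will be trained to control a cursor on a computer screen using motor-related cortical activity". Training runs for up to 15 sessions, at two or three visits a week. Item 1a lists the outcome times: "Time (baseline, mid, post, 1 month post) as the within-participant factor".

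**The concern.** The split compares patients by something that happens to them after randomisation. The adaptive randomisation balances age and ARAT severity between the arms, but it does nothing to balance high against low performers within one arm. Two non-causal routes to a difference are therefore open.

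- **Reverse causation.** The BCI is driven by EEG recorded while patients move, or try to move, the affected hand. A patient whose hand is improving for any reason, including FES or practice, may give a clearer signal in later sessions. Performance is then partly a result of recovery.
- **A shared cause.** Milder impairment or a smaller lesion may give both better BCI control and more gain.

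Under either route the rule in 1b would credit synchronization for a difference it did not cause. What is at stake is the mechanistic conclusion of the trial, since 1b is the plan's stated test of synchronization.

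**Working it through.** **1. Inputs.** Active arm n = 72 (Randomization section), so about 36 against 36 after a median split. ARAT difference of 6 points and SD 12 from pre to post (Sample size considerations). Two-sided alpha of 0.05 is assumed, because the documents do not state it. No correlation between BCI performance and gain is given, so a range is shown.

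**2. The plan's own figure.** Item 1b has no calculation of its own. The only design figure is 44 per age-by-severity cell with 90% power. It reproduces as a within-group pre-post test with d = 6/12 = 0.5: the normal formula gives (12 × (1.960 + 1.282)/6)² = 42.03, so 43, and the t-based calculation gives 44 with power 90.0%. This supports reading 12 as the SD of change.

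**3. Time order, from the text.** The BCI task is described within the training sessions. Those sessions lie between baseline and post, and the sample-size section uses change from pre to post. Overlap of exposure and outcome is the natural reading, but item 1b does not state it.

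**4. Size of a non-causal difference.** Suppose performance and gain are jointly normal with correlation r, arising from reverse causation or a shared cause, and BCI has no effect. The halves of a median split differ by 2 × √(2/π) = 1.596 SD in performance, so gain differs by r × 12 × 1.596 = 19.15 r points. A difference of 6 points needs r = 6/19.15 = 0.31.

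For r = 0.3 the difference is 5.7. The within-group SD is 12 × √(1 − 0.637 × 0.09) = 11.65, the standard error is 11.65 × √(2/36) = 2.75, and the ratio is 2.09 against a critical value near 1.99. That gives roughly a 53-54% chance of rejection. Simulation (20,000 runs per cell):

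| r | Mean difference, ARAT points | Rejection, n = 72 | Rejection, n = 64 (about 10% loss) |
|---|---|---|---|
| 0 | 0.0 | 5% | 5% |
| 0.1 | 1.9 | 10% | 9% |
| 0.2 | 3.8 | 27% | 24% |
| 0.3 | 5.7 | 53% | 49% |
| 0.4 | 7.6 | 80% | 74% |

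The rejection rates do not depend on the SD of 12; the point differences do.

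**5. Reverse causation session by session.** Assume that gain accrues linearly over 15 sessions, BCI has no effect, stable skill and session noise each have SD 1, and the signal rises by λ per SD of recovery to date. For λ = 0.25, 0.5, 0.75 and 1.0:

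- Performance averaged over all 15 sessions: rejection 10%, 31%, 59% and 83%, with differences of 2.1, 4.2, 6.1 and 7.8 points.
- First session only: about 5% throughout.
- Sessions 1 to 3: 5-7%.

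Variants of the model give 10-29% at weak feedback and 31-82% at moderate feedback. Keeping performance continuous does not cure this. In one variant the median-split test rejected in 21-29% (weak) and 66-82% (moderate), and the continuous analysis in 33-46% and 83-96%.

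**6. What time ordering achieves.** Take performance before the mid visit against post ARAT, adjusted for mid ARAT, again with no BCI effect.

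- ARAT measured without error: rejection 4.6-5.8%.
- ARAT measured with error: from 3.6% up to 29% across the settings tried. With error SD at 0.5 to 1 times the SD of half-period gain, and strong feedback with half-gains correlated 0.5, it was 17-29%.
- A shared cause of skill and gain: 58% in one setting, against 74% for the 1b t-test.

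**The case against.** The strongest reply is that the overlap is inferred. A reader might take the plan to say that performance and change are measured over the same weeks, but item 1b names neither window. First-session performance would fit its words, and step 5 shows that this choice largely removes reverse causation. The EEG analysis paragraph also mentions a screening phase; whether that yields a classification score is not stated. This part stands: the overlap is a natural reading, not a stated fact.

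A reader might also infer that the false difference will arise, or that the highest rejection rates apply to this trial. The documents do not support that. Every feedback strength and correlation above is assumed. The EEG measures that Aim 2 relates to intervention or to behavioral change are laterality, r-squared and coherence, not classification performance. They make a link plausible without measuring it.

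The background notes that chronic patients may have little prospect of spontaneous recovery. That weakens one source of gain, but gain from FES or practice is enough for the argument.

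Finally, a reader might infer that a time-ordered analysis would restore the causal claim. Step 6 shows that it would not.

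Item 1b is post hoc and confined to one arm, which limits the consequence. It does not excuse a decision rule that is causal as written.

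**Conclusion.** The point holds as a defect in the stated decision rule. A difference between high and low performers cannot, by itself, be evidence that synchronization contributes to recovery, because the comparison is not randomised, not ordered in time and not adjusted. Under assumed correlations of 0.1 to 0.4 with no BCI effect, the test would support the plan's conclusion in roughly 10% to 80% of trials rather than 5%, and a correlation near 0.31 is enough to produce the plan's own 6-point difference. These figures rest on 72 evaluable active-arm patients, joint normality, a two-sided 5% level and correlations that the documents do not supply.

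The companion rule for a null result is also weak: 36 against 36 has about 55% power for 6 points at SD 12. Neither problem touches the randomised comparison in 1a.

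**What to change.** 1. Replace the decision rule in 1b, in both directions. Say that any difference is an association between BCI performance and outcome change, for every version of the analysis, and that a null result does not separate the two explanations.
2. State which sessions define performance and which interval defines change.
3. Add a time-ordered analysis. The exposure is BCI performance in sessions before the mid assessment, kept continuous. The outcome is ARAT at post and at 1 month post, adjusted for baseline and mid ARAT, plus age and lesion volume where available. MRI is optional, so lesion volume will be missing for some patients.
4. State its limits: it reduces reverse causation but removes neither confounding nor the effect of ARAT measurement error.

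The cost is analysis-plan wording and no new visits, since the mid assessment already exists. The time-ordered analysis uses only early sessions and later gain, so it has less power. In one assumed model, power for a modest true effect fell from 45% to 27%.

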Stroke Rehabilitation Using BCI Technology

February 1, 2022

NCT04141774

RESEARCH PROTOCOL

Stroke Rehabilitation Using BCI Technology

PI: [name] M.D. Ph.D., Associate Professor, Department of Radiology, UW-Madison.
[contact]

Co-I: [name] Ph.D., Professor, Department of Biomedical Engineering, UW-Madison.
[contact]

Co-I: [name], Assistant Professor, Department of Orthopedics and Rehabilitation,
UW-Madison

Protocol Version Date: February 1, 2022

Funding Sponsor: NIH

Project Summary

The aim of this study is to determine if functional muscle stimulation, directed by electroencephalogram (EEG) output, can increase the extent of stroke recovery on behavioral measures and induce brain plasticity as measured by functional magnetic resonance imaging (fMRI). Study procedures proposed have been extensively used in our lab for a previously approved study (under approval #2010-0004 and 2015-0439).

Background and Significance

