Neuroplasticity or Brain plasticity, defined as the brain's ability to acquire new skills and adapt to a new environment, is a fundamental mechanism underlying functional recovery after stroke and other forms of brain injury or with natural ageing (Cramer et al., 2011). Although BCI systems are being increasingly used in studies of motor recovery after stroke, TBI, and other spinal cord injuries, we do not yet understand the brain mechanisms underlying recovery. The motor system constantly adapts to external changes so as to achieve optimum motor performance. Our ongoing study (Young et al., 2014, 2015, 2016; Song et al., 2014, 2015, 2016) suggests that noninvasive Electroencephalography(EEG) driven Brain Computer Interface (BCI) systems hold the potential for facilitating recovery in the chronic phase after stroke by synchronizing central or brain activity with peripheral movements and thereby harnessing brain plasticity. These studies confirm that change in the pattern of brain activity that is linked to affected hand movement leads to motor re-learning and induces brain plasticity or reorganization that could lead to improvement in motor function (Ang et al., 2013; Prasad et al., 2010; Shindo et al., 2011). This is of special importance for patients in the chronic phase of recovery that may have little to no spontaneous recovery potential of the affected arm. Given that these patients have also likely exhausted other forms of intervention available to them through proper healthcare channels, it is imperative to explore novel intervention technologies that have shown some promise in this population. In order to be accepted and integrated into regular rehabilitation practice, it is necessary to establish the efficacy of the EEG-BCI approach in a prospective randomized control trial with a larger cohort using well-validated outcome measures. Moreover it is necessary to establish efficacy compared to standard accepted modes of intervention that focus on peripheral or passive movement repetition such as that provided by using functional electrical stimulation of the impaired arm. A recent review and meta-analysis of 18 randomized control trials found that functional electrical stimulation (FES) had a modest effect on activity compared with no intervention or placebo (Meilink et al., 2008). While passive movement repetition can be an effective rehabilitation strategy, the recovery can be slow, painstaking and suboptimal. However few trials have compared the effects of standard FES matched in dose and duration to that provided by novel brain based intervention technologies such as EEG-BCI-FES. Our proposed study will determine the efficacy of active (brain-based or EEG-BCI) FES vs. passive FES in a large size cohort of chronic stroke patients using a prospective randomized well-controlled longitudinal study design and will assess concomitant brain (task fMRI, resting fMRI, and Diffusion Tensor Imaging (DTI)) and behavioral changes in these patients.

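### Item 1b credits any high-versus-low BCI difference to synchronization, although the split is not randomized, the test is unadjusted, and the amount of FES delivered is neither specified nor measured

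*Combined protocol and SAP*

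**What the plan says.** Under Data Processing/Data Analysis, For Specific Aim 1, item 1b is a post hoc analysis confined to the active FES group. The grouping is: "A median split of high to low performers on the BCI task will be done". Changes in outcome are then compared "using unpaired t-tests", and no covariate is listed. The plan equates poor performance with weak coupling: "low performance on the BCI task (when there is less synchronization between the BCI and FES".

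Both possible results are given a meaning in advance. For a difference: "If there is a difference in the two groups then this is evidence that BCI synchronized to FES contributes to recovery". For no difference: "if there is no difference then this is evidence that BCI irrespective of synchronization to FES contributes to recovery".

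On the device, the Project Summary describes "functional muscle stimulation, directed by electroencephalogram (EEG) output", and the Active FES paragraph under C) Intervention says "The EEG-BCI system will be connected to a FES device and the FES electrodes will be placed on the stroke-affected arm". That paragraph has the stimulation level recorded. Nowhere do the documents say what BCI result triggers or withholds stimulation, how many stimulations a patient receives, or for how long. Sessions have a ceiling of 15 rather than a fixed number.

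**The concern.** The first decision sentence is valid only if high and low performers differ in nothing else that affects recovery. Nothing in the design secures that. Randomization balances the two arms, not two halves of one arm formed afterwards from the patients' own performance.

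Two kinds of rival explanation are open:

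- **Patient factors.** Age and ARAT severity are important enough to be the randomization factors, yet 1b ignores both. Either could influence how well a patient operates the BCI and how much the arm recovers.
- **FES amount.** Stimulation in this arm is driven through the BCI, so patients who succeed more often may also receive more stimulation. If they do, performance and FES amount rise together and the t-test cannot tell them apart. Making FES equal between the two arms would not help, because both halves are in the active arm.

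Item 1b is the only analysis that tries to isolate synchronization; item 1a compares whole treatment packages. Followed as written, 1b could publish a mechanistic claim that its data cannot carry.

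**Working it through.** **The plan's own figure.** No figure is given for 1b. The only calculation, under Sample size considerations, is 44 per age-by-severity cell for 6 ARAT points, SD 12 and 90% power. A paired t-test with standardized effect 6/12 = 0.5 at a two-sided 5% level (my assumption; the level is not stated) gives 43.995, so 44. It reproduces and is not in dispute. I use it only as the source of the SD and the 6-point scale.

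**Inputs from the plan.** Active arm 72 (Randomization), so 72/2 = 36 per half; SD 12; 6 points.

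**Inputs assumed.** The true synchronization effect is zero. Any link between performance and FES amount, and between FES amount and ARAT change, is assumed, because the documents give neither.

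**Calculation A: proportional model.** Suppose the mean gain is 6 points and proportional to FES delivered, and FES delivered is proportional to BCI accuracy, with a mean accuracy of 70%.

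- SE of the difference = 12 × √(2/36) = 2.83.
- Difference from FES amount alone: d = 6 × (high − low)/0.70.
- Chance of a significant result = Φ(d/2.83 − 1.96) + Φ(−d/2.83 − 1.96).

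| Accuracy, low v high | d (points) | Significant |
|---|---|---|
| no link with amount | 0 | 5% |
| 60% v 80% | 6 × 0.20/0.70 = 1.7 | 9% |
| 55% v 85% | 6 × 0.30/0.70 = 2.6 | 15% |
| 50% v 90% | 6 × 0.40/0.70 = 3.4 | 23% |

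**Calculation B: correlation model.** Let r1 be the correlation of performance with FES amount and r2 that of FES amount with ARAT change. The expected high-minus-low difference is about 12 × r1 × r2 × 2√(2/π) = 19.1 × r1 × r2. For r1 = 0.5 and r2 = 0.2 this is 1.9 points. For r1 = 1.0 and r2 = 0.5 it is 9.6 (9.5 when simulated). With 72 patients, a median split and 5,000 simulated trials per cell, the t-test was significant this often:

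| r1 | r2 = 0.2 | 0.3 | 0.4 | 0.5 |
|---|---|---|---|---|
| 0 | 4% | 5% | 5% | 5% |
| 0.5 | 10% | 17% | 26% | 38% |
| 0.8 | 18% | 37% | 58% | 80% |
| 1.0 | 27% | 53% | 80% | 95% |

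**Effect of adjustment.** With FES amount added to the model, the rate was about 5% in every cell. That result depends on the simulation containing no other confounder. The variance of the high/low term rises by 1/(1 − c²) with c = r1√(2/π): 1.2, 1.7 and 2.8 for r1 = 0.5, 0.8 and 1.0. If performance is entered as a continuous score, the factor is 1/(1 − r1²): 1/0.75 = 1.3 at r1 = 0.5, 1/0.36 = 2.8 at 0.8, and not estimable at 1.0.

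**The null result.** With 36 per half, power for 6 points is 56%, and 80% power needs a true difference of 7.9 points. A non-significant result therefore cannot support the plan's second decision sentence either.

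Confounding by severity and age is not quantified here. The documents give no figure relating either to BCI performance.

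**The case against.** The strongest objection is that the FES route is an inference. A reader might take from the device description that BCI success determines how much FES a patient gets. The documents do not say so. They state that EEG output directs the stimulation and that the two devices are connected, but give no trigger rule. The plan's description of low performance as reduced synchronization fits a system in which only timing varies. If rest misclassified as movement also triggers stimulation, low performers need not receive less. In either case this route closes. The objection stands: the point is that the protocol leaves the matter open and 1b does not check it.

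A reader might also infer that Background and Significance makes dose matching a condition that 1b breaks. It does not. The remark that "few trials have compared the effects of standard FES matched in dose and duration" describes a gap in the literature on comparisons between therapies, and the small FES benefit cited there is against placebo or no treatment. It is not a dose-response among patients who all receive FES.

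Third, 1b is post hoc and secondary. The randomized comparison in 1a is untouched, so nothing here weakens the trial's efficacy analysis. That limits the importance of the point, but the label does not excuse a causal reading fixed in advance.

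Finally, adjustment is no cure. If performance largely determines FES amount, the covariate lies on the path from performance to outcome and is nearly collinear with it. Nor would a performance term that survives adjustment for FES show synchronization to be the cause, since severity, cognition or motivation could still explain it. This stands too, which is why the conclusion has to change as well as the model.

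**Conclusion.** The concern holds in a limited form. A difference between halves formed after randomization, tested without covariates, is not evidence that synchronization contributes to recovery, and the plan commits to reading it that way. This does not depend on how the device works.

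The size of the FES-amount problem does depend on that. The 9% to 23% range rests on assumed accuracies and on a 6-point gain produced wholly by FES. The wider 10% to 95% range rests on assumed correlations (r1 of 0.5 or more, r2 of 0.2 or more). If amount is unrelated to performance, the rate is about 5%. These figures show what could happen and do not estimate what will. All of them assume 36 analysable patients per half.

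**What to change.** 1. State in the Active FES section whether the amount of FES delivered depends on BCI success. This asks for the existing rule to be documented, not changed.
2. Log the number and duration of stimulations per session for each patient.
3. In 1b, replace the t-test with a regression of change on BCI performance that includes baseline ARAT and age. Fit a further model adding delivered FES amount. Report FES amount by performance level.
4. Reword the decision sentences. A difference is reported as an association of BCI performance with recovery or, if the two cannot be separated, of performance together with the FES it delivers. It is not reported as evidence that synchronization is the cause. A non-significant result is reported with its confidence interval, without the conclusion now attached to it.

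**Cost.** Baseline ARAT and age are already collected, and no extra visits are needed. The log should be a small addition, but PC control of the stimulator is described only in the passive-arm paragraph, so the sponsor should confirm that the active-arm set-up can record it. The statistical price is the wider interval for the performance term (variance up about 1.2 to 2.8 times for the high/low term, more for a continuous score that almost determines FES amount) and a more modest claim from a secondary analysis.

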Passive FES (the control group): Functional Electrical Stimulation (FES) of the upper extremity is delivered through a pair of 2” x 2” square electrodes, commercially available stimulus isolator units, which ensure clean, opto-electrical isolation, placed securely on the affected forearm using highly conductive Electrolyte Spray and produced by the LG-7500 Digital Muscle Stimulator (LGMedSupply, Cherry Hill, NJ, USA). The electrodes are placed in half the sessions, superficial to flexor digitorum superficialis to facilitate hand and finger flexion, and in the other half of the sessions superficial to extensor digitorum communis to facilitate hand and finger extension.

Stimulation is controlled through the PC using an Arduino Uno R3 (Adafruit Industries, New York, NY, USA) and a simple reed relay circuit, with the amplitude set to elicit observable muscle activation (e.g. finger grasping) without pain. The pulse rate of the stimulation is set to 60Hz in order to produce tetanic contraction of the muscle and the pulse width is set to 150 μ s. The input signal will initially be set to zero and adjusted in steps of 5 mA, with allowable stimulation up to 50 mA. All parameters will be adjusted to the patients’ comfort level, and testing will be interrupted immediately should a patient report any discomfort.

Training will involve trials of actual or attempted hand movement alternating with periods of rest. Brain activity will be simultaneously recorded using EEG (electroencephalography) technique. EEG electrodes will be attached to the patient’s scalp using a standard, commercially available electrode cap.

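### Aim 1b counts either result of the high- versus low-performer comparison as evidence that BCI contributes to recovery, with no non-BCI comparator

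*Combined protocol and SAP*

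**What the plan says.** Under Data Processing/Data Analysis, Specific Aim 1, item 1b is a post hoc analysis confined to the Active FES group. Its stated purpose: "This will allow us to assess to what extent BCI synchronization to FES leads to improved stroke recovery". The method: "A median split of high to low performers on the BCI task will be done", followed by unpaired t-tests of change in the outcome measures. The comparison group is "those with low performance on the BCI task (when there is less synchronization between the BCI and FES", so low performers are still treated with BCI and FES.

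Two readings are fixed in advance:

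- Difference found: "If there is a difference in the two groups then this is evidence that BCI synchronized to FES contributes to recovery".
- No difference found: "if there is no difference then this is evidence that BCI irrespective of synchronization to FES contributes to recovery".

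The plan gives 1b no equivalence margin, power, covariate adjustment or condition on the result of 1a. The passive FES arm enters only the mixed model in 1a.

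**The concern.** The two readings cover every possible result. They differ on whether synchronization matters, but both conclude that BCI contributes to recovery. On that second question 1b cannot come out negative.

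Each reading also has its own weakness. Without a non-BCI group, equal change in the two halves is also what one would see if FES alone or practice produced the recovery and BCI did nothing. A non-significant t-test does not show that two groups are the same. A significant one between self-selected halves does not show that synchronization caused the gap.

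At stake is a report that credits BCI with recovery when the randomised comparison shows no benefit, or that dismisses a real synchronization effect.

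**Working it through.** **1. The logic, which needs no numbers**

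| t-test result | Plan's reading on synchronization | Plan's reading on BCI | What the data could also mean |
|---|---|---|---|
| Difference | It matters | BCI contributes | Better-prognosis patients perform better on the BCI task |
| No difference | It does not matter | BCI contributes | FES alone or practice, no BCI effect, or too few patients |

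The Intervention section shows why the alternatives are live. Of the passive FES group it says "Training will involve trials of actual or attempted hand movement alternating with periods of rest", and of the active group "Electrode placement is similar to that described above for the patients in the passive FES group". Movement practice and peripheral stimulation are thus common to both arms, and only the 1a contrast separates BCI from them.

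Suppose BCI has no effect and performance is unrelated to recovery. A 5% test then gives no difference in 95% of trials and a difference in 5%. The plan credits BCI in 95% + 5% = 100% of them.

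**2. Inputs for the size of the problem**

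- Active arm 72 (Randomization), so 36 v 36. With the 10% loss in Sample size considerations, 72 × 0.9 = 64.8, taken as 32 v 32.
- SD 12 and 6 points: the pre-to-post ARAT figures in Sample size considerations. They reproduce the plan's own 44 per cell: a two-sided paired t-test at 0.05 with 6/12 = 0.5 and 90% power needs 43.995. That supports reading 12 as the SD of within-patient change. The plan gives no effect size for 1b, so a 6-point gap between halves is illustrative.
- Two-sided alpha 0.05: assumed; none is stated.

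**3. Chance of missing a true 6-point gap, per outcome**

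SE = SD × √(2/n); noncentrality = 6/SE; power from the noncentral t with 2n − 2 df.

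- 36 v 36: SE = 12 × √(2/36) = 2.83; noncentrality 2.12; power 0.553; missed 44.7%.
- 32 v 32: SE = 12 × √(2/32) = 3.00; noncentrality 2.00; power 0.504; missed 49.6%.
- SD 10: missed 29% / 34%. SD 14: missed 57% / 61%.

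The 95% CI half-width is 1.994 × 2.83 = 5.6 points (36 v 36) or 1.999 × 3.00 = 6.0 (32 v 32). In simulation (400,000 trials), 94% / 95% of the non-significant results still had 6 points inside the 95% CI.

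**4. What a margin would do**

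Require the 90% CI to lie within ±6 before saying that synchronization does not matter (SD 12, simulated):

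- True gap 6: the wrong statement falls from 45% / 50% to 4.5% / 4.0%.
- True gap 0: 95% of results would get the null reading under the plan, but only 35% / 26% would meet the margin (SD 10: 62% / 53%; SD 14: 13% / 7%).

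**5. The difference reading**

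The halves are formed after randomisation and compared unadjusted. With zero BCI effect, but performance correlated 0.2 / 0.3 / 0.5 with change through prognosis (assumed values, 36 v 36), a difference appears in 27% / 53% / 95% of simulated trials. The opening sentence of 1b expects high performers to do better, but the decision sentence accepts a difference in either direction.

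**6. The median split**

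Assume a normal score linearly related to change, with the high-low gap 6 and within-half SD 12 (correlation 0.304). Power is 54% / 49% with the split and 75% / 69% with the continuous score. The split therefore makes the null reading more likely.

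**The case against.** The strongest defence is that 1b asks only about synchronization and follows 1a. Read as a follow-up to a positive 1a, it can take its non-BCI comparator from there, and the null sentence then says only that an established benefit does not depend on synchronization. This would soften the point, but the plan states no such condition. Even with one, a non-significant test without a margin cannot support the claim about synchronization.

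Second, 1b is labelled post hoc and changes no primary estimate, sample size or procedure. That is true and limits the severity. It does not excuse fixing causal readings in advance.

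Third, the numbers are borrowed: 6 points and SD 12 describe pre-to-post change, the 10% loss comes from the calculation for 192 rather than 144 participants, and the rates apply to one outcome at a time. All of this stands, and the figures are illustrations. The logical fault depends on none of them.

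Fourth, the gain from regression rests on normality and linearity, and a floor, ceiling or threshold in BCI performance would change it. The plan also does not define the performance score, but the median split needs that definition just as much. Regression is therefore a preference and not the essential correction.

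**Conclusion.** The concern holds. As written, 1b cannot yield evidence against a BCI contribution, and it uses no comparison that could test one. This follows from the text alone.

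The null reading is also unreliable on its narrower question. For a true 6-point gap it would be wrong about 45% to 50% of the time at SD 12, and 29% to 61% across SD 10 to 14 and the two sample sizes, assuming two-sided alpha 0.05. The difference reading supports an association only.

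This should be fixed. It is confined to an exploratory analysis; the randomised 1a comparison is unaffected.

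**What to change.** 1. Delete both clauses that say what the result is evidence of.
2. State that whether BCI contributes to recovery is judged only from the randomised active versus passive comparison in 1a.
3. Report 1b as an exploratory association with its 95% CI. Say that synchronization does not matter only if the interval lies within a margin stated in advance, together with the CI level used for that check.
4. Preferably, replace the median split and t-tests with a regression, in the Active arm, of each outcome on continuous BCI performance. Adjust for baseline ARAT and age (the plan's own randomization factors), and for the baseline of the outcome when it is not ARAT. Define the performance score whichever analysis is kept. Adjustment does not make performance a randomised variable, so the result remains an association.

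The cost is SAP wording and one regression per outcome on data already collected, with no change to recruitment, visits or 1a. Item 3 requires a margin to be chosen and justified, and many null results will not meet it. Item 4 adds a linearity assumption, which can be checked with a plot.
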